4.3.3.4 Adverse Events (AE)

All observed or volunteered adverse events regardless in the treatment group or suspected causal relationship to the investigational device are captured in the EDC. The adverse events will be coded using Meddra Coding.

4.3.3.5 ECG

ECG is captured in the EDC and will be reported.

4.3.3.6 Vital Sign

Vital signs, including blood pressure, are captured in the EDC and will be reported.

4.4 STATISTICAL Analyses

4.4.1 Study Days

Days as defined in the protocol (and in SAP section 3.3.1) will be used.

Additionally, for the calculation related to infusion set insertion, Day 0 will be the day of insertion.

4.4.2 General Consideration of Descriptive Summary

The following rules will be used, unless specific described, for any descriptive summary.

1. Descriptive summary will be by treatment and by period
2. For continuous variables: mean, SD, median, minimum and maximum will be reported. Two decimal points will be used unless specified.
3. For category variables: count, percentage, and the total used as a denominator will be reported. One decimal point will be used unless specified.

4.4.3 Baseline Characteristics Analyses

4.4.3.1 Demographics

Demographics table includes summaries for age, sex, race, and euthenics. A descriptive summary will be provided.

Population	ITT
------------	-----

4.4.3.2 Subject Disposition

Subject disposition will be presented descriptively. It will show the # of subjects using each device.

Population	ITT
------------	-----

4.4.3.3 Physical Exam

The physical exam includes height, weight and a systematic body exam. A descriptive summary will be provided.

Population	ITT
------------	-----

4.4.3.4 Medical History

The physical exam includes a pregnancy test, The medical history includes the patient’s insulin correction factor and previous medical conditions. A descriptive summary will be provided.

Population	ITT
------------	-----

4.4.3.5 Prior and Concomitant Medications

Both prior and concomitant medications will be listed.

Population	ITT
------------	-----

4.4.4 Efficacy analyses

4.4.4.1 Analyses of Primary Endpoints

Our primary endpoint is the failure rate of infusion set. A descriptive summary of infusion set failures will be provided. The summary will be reported for each period.

The $AUC_{0-300(GIR)}$ on day of insertion (day 0) and days 3, 5, 7 in periods 1 and 2 will be calculated using the trapezoidal rule as described in section 4.3.2.1.

The nature log of AUC: $\ln(AUC_{0-300(GIR)})$ will then be calculated.

A mixed-effects (repeated-measures) linear model with *treatment* and *period* as fixed effects and participant as a random effect will then be fit to this data. Estimates of the slopes by treatment will be generated as contrasts based on the least squares means. The contrast is: the difference in slopes (control minus Achilles) of $AUC_{0-300(GIR)}$ versus day, computed from the least squares means of $AUC_{0-300(GIR)}$ at each study day within each of the 2 periods.

Treatment comparisons and confidence bounds on the difference in slopes will be presented.

The primary analysis will be conducted on the ITT population using all available data within the mixed model repeated measures framework. Missing an $AUC_{0-300(GIR)}$ assessment will be assumed missing at random (MAR). However, a sensitivity analysis will be done to check the extent to which the missing data could have made a difference in the conclusions of the analysis.

Additionally, the same analyses will be repeated on the baseline adjusted AUC_{0-300} and ITT population.

Population	ITT and PP (ITT is the primary , PP is the sensitivity)
------------	---

4.4.4.2 Analyses of Secondary Endpoints

4.4.4.2.1 Daily Insulin Infusion Set Survival Rate

The survival of the Achilles and control infusion sets will be compared using a discrete lifetable analysis over study days 0, 3, 5, and 7 and the discrete form of the log-rank test.

4.4.4.2.2 PK Parameters

All pharmacokinetic parameters will be presented descriptively.

Additionally, AUCs, t_{50} , C_{max} , t_{max} , and MRT will be tested for treatment effects. The effects between Achilles and control set will be compared in a mixed-effects (repeated-measures) linear model with *treatment* and *period* as fixed effects and *participant* as a random effect. Log-transformation will be applied if data distribution is found to be highly skewed.

The mean difference between treatments (or on the log-scale) will be compared with a two-sided test using significance level $\alpha=0.05$. Then mean ratio and its 95% confidence interval will be calculated

- Inverse-transforming will be done if the variable was log-transformed.

Population	ITT and PP (ITT is the primary , PP is the sensitivity)
------------	---

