3.4 SAMPLE SIZE JUSTIFICATION

A sample size of 24 participants is sufficient to generate 90% power for a 2-tailed $p=0.05$ comparison of the $\ln(\text{AUC}_{0-300(\text{GIR})})$ slope contrasts (=control minus Achilles), within this 2x2 crossover design. In addition to the usual regularity assumptions for the 2x2 crossover design (i.e. no carryover effects), this computation was based on the following assumptions:

1. The $\ln(\text{AUC}_{0-300(\text{GIR})})$ values are normally distributed.
2. The within participant variance is 40% of the total variance.
3. The study day correlation matrix of the within-participant $\ln(\text{AUC}_{0-300(\text{GIR})})$ assessments is AR (autoregressive model) with correlation $r=0.5$.
4. The within plus among participant variance for the $\ln(\text{AUC}_{0-300(\text{GIR})})$ values is 0.21 (based on previous studies).
5. The difference in slopes (Achilles minus control) is at least 0.07.

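### The PK and PD device tests name participant as the only random effect; if the four clamps per set are pooled, the error term for the device comparison is missing and, on the plan's own correlation, a 5% test runs at about 10% to 22%.

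*SAP*

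**What the plan says.** SAP 4.4.4.2.2 (PK) and 4.4.4.2.3 (PD) test AUCs, half-maximum times, peak, time to peak, and residence time or duration of action at a two-sided 5% level. The model is a "mixed-effects (repeated-measures) linear model with *treatment* and *period* as fixed effects and *participant* as a random effect". Both sections then describe one average device difference per parameter. Neither names a day term, a participant-by-period effect, a residual covariance or a degrees-of-freedom method. Protocol 9.4.3 states the same model. SAP 4.4.4.1 uses the same list for the primary endpoint, with treatment and period "as fixed effects and participant as a random effect will then be fit to this data".

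The sample-size section (SAP 3.4) does not treat clamps as independent. Its third assumption is that the correlation matrix of the within-participant "assessments is AR (autoregressive model) with correlation" 0.5. It does not say whether the lag is counted in visits or in days.

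Under Protocol 6.1.1.6, the later visits of a period repeat the Visit 1 procedures but not the insertion of the catheter. The clamps on days 0, 3, 5 and 7 therefore go through one set at one site.

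**The concern.** In a 2x2 crossover, device changes only between the two periods of a participant. The right yardstick for the device difference is how much a participant's period average varies from one period to the other. A participant intercept alone does not carry that variation. It treats the four readings through one cannula as four independent replicates of the device.

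With exactly seven participants and all 56 clamps, the intercept-only model leaves 56 − 9 = 47 residual degrees of freedom. The crossover comparison has 14 − 9 = 5.

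At stake are the between-device p-values and intervals for the tested PK and PD parameters. SAP 4.4.4.2.3 makes no correction for multiple tests. SAP 2.5 and 5 make these the final analyses after early termination.

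**Working it through.** **Inputs.** SAP 3.4: total variance 0.21; "The within participant variance is 40% of the total variance", so 0.40 × 0.21 = 0.084; autoregressive r = 0.5. SAP 4.4.4.1: days 0, 3, 5, 7 in two periods. Sample sizes: 24 (planned, SAP 3.4) and 7 (completers at termination, SAP 2.5).

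**The plan's own figures.** For these tests the only stated figure is the 5% level. With independent clamps, simulation of the model as written gives 5.0% at n = 24 and 4.9% at n = 7, so the nominal level is reproduced when the omitted correlation is zero. SAP 3.4 also says: "A sample size of 24 participants is sufficient to generate 90% power for a 2-tailed $p=0.05$ comparison" (of slopes). Its listed inputs give more than that. With lag per visit the slope variance is 0.003061, the standard error is √(2 × 0.003061/24) = 0.0160, and 0.07/0.0160 − 1.96 = 2.42, which is 99% power. This is a separate matter, conservative in direction, and does not bear on the present point.

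**Step 1: average correlation of the four clamps in a period.**
- Lag per visit: lags 1, 2, 3 occur 3, 2, 1 times. (3 × 0.5 + 2 × 0.25 + 0.125)/6 = 0.354.
- Lag per day: gaps 3, 2, 2, 5, 4, 7 days. (0.125 + 0.25 + 0.25 + 0.03125 + 0.0625 + 0.0078)/6 = 0.121.

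**Step 2: true against modelled variance of the device difference.** The true variance of a period mean is (1 + 3ρ)/4 times the within-participant variance. The intercept-only model estimates a residual of about [6(1 − ρ) + (1 + 3ρ)]/7 = 1 − 3ρ/7 and divides it by 4.
- Per visit: 2.0625/0.848 = 2.43.
- Per day: 1.363/0.948 = 1.44.

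**Step 3: large-sample type I error.**
- Per visit: P(|Z| > 1.96/√2.43) = P(|Z| > 1.26), about 21%.
- Per day: P(|Z| > 1.96/√1.44) = P(|Z| > 1.63), about 10%.

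**Step 4: simulation** (complete data, no day trend, residual-df t test).

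| Analysis | n | Lag per visit | Lag per day |
|---|---|---|---|
| Pooled, as written | 24 | 21.4% | 10.4% |
| Pooled, as written | 7 | 21.8% | 10.4% |
| Pooled, participant-by-period effect added | 24 | 5.0% | 5.1% |
| Pooled, participant-by-period effect added | 7 | 5.2% | 5.1% |
| One study day at a time | 24 | 5.0% | 5.1% |
| One study day at a time | 7 | 5.1% | 4.8% |

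A Wald z test in place of t raises the n = 7 figures to 23.0% and 11.3%.

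**Step 5: what changes the size.**
- *Common decline over days, no day term.* The trend enters the residual and widens the standard error. At 0.035 per day (log scale) the rates are about 18–20% (per visit) and 8–9% (per day). At 0.07 per day they are about 12–13% and 4–5%.
- *Set failures.* With half the sets lost by day 7: about 19% and 8–9%.
- *n − 2 degrees of freedom, same model, no trend.* 8.8–19.2% at n = 24 and 3.9–11.9% at n = 7.
- *Other correlations, lag per visit, n = 24.* About 7% at r = 0.1 and 31% at r = 0.7.
- *Primary slope contrast.* About 5.5–7%, because a slope within a set does not depend on the level of that set. The exact value depends on how day enters the model.

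**The case against.** The strongest reply is that pooling is inferred. The protocol synopsis defines these endpoints partly as treatment differences at given times, and the SAP objectives list the four days. Fitted to one day at a time, the stated model is the ordinary crossover model and holds 5%. The exploratory model in Protocol 9.4.9 adds day, so leaving day out here is compatible with by-day testing.

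The effect list is also plainly shorthand. SAP 4.4.4.1 uses the same list but needs least squares means at each study day, which cannot be had without day terms. It also refers to a repeated-measures framework, under which a programmer might fit a residual covariance.

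These points stand as limits. A reader might infer that the tests will run at 10–23%, or that every device p-value is too small. The documents do not support either statement, for four reasons:
- They do not fix pooling or the covariance.
- They give r = 0.5 only for ln AUC of the glucose infusion rate, not for insulin concentrations or timing parameters.
- The trial expects a decline over days, and an unmodelled decline can bring the rate down to about 5% under the per-day lag.
- The 47 degrees of freedom assume exactly seven participants with every clamp. The ITT set needs only one clamp and may be larger, and Protocol 9.4.1 expects 40–50% of sets to fail.

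The reply does not remove the problem. Both SAP sections describe one device difference per parameter and mention no by-day fit. By-day tests would leave one value per set, with no serial measurements inside a period for the repeated-measures label to describe. The effects that are listed include nothing for the set. Fitted as written to all clamps, the rule gives the wrong error term.

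**Conclusion.** The point holds conditionally. If the clamps are pooled, the stated model lacks the participant-by-period error that the device comparison needs. With r = 0.5, complete data and no day trend, a nominal 5% test runs at about 10% (lag per day) to 22% (lag per visit), at both 7 and 24 participants. With an unmodelled common decline of 0.035–0.07 per day, the ranges are about 4–9% and 12–20%. Set failures lower the inflation modestly. For PK parameters the correlation is an assumption.

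If the tests are run by study day, there is no inflation. A reader might also infer that the primary result is compromised. It is not, to any material degree, since the slope contrast runs at about 5.5–7%. The affected tests are secondary, so this should be fixed but does not threaten the primary analysis.

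**What to change.** In SAP 4.4.4.2.2 and 4.4.4.2.3, state whether the device tests are run by study day or pooled over the four clamps.

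If pooled:
- Add day as a fixed effect, and treatment-by-day where by-day contrasts are wanted. Day alone is not enough: it takes the trend out of the residual and so returns the test to the no-trend figures of about 10–22%.
- Add a random participant-by-period effect, or name an AR(1) or spatial-power residual in day within participant-by-period.
- Use Kenward-Roger degrees of freedom.
- Use the same covariance in 4.4.4.1 for consistency.

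Do not substitute simple set means. They are equivalent only with complete data. With 40–50% of sets expected to fail, the means would average different days and mix device with day.

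The cost is a few lines of SAS and wider, correctly sized intervals. On the no-trend, complete-data figures, the standard error grows by √1.44 = 1.20 to √2.43 = 1.56. With seven complete participants the critical value also rises, from 2.01 (47 df) to 2.57 (5 df), a further factor of 1.28.

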4.4.4.2.3 PD Parameters

All PD parameters will be presented descriptively.

Additionally, AUCs, t_{50} , GIR_{max} , $t_{max(GIR)}$, and Duration of Insulin Action will be tested for treatment effects. The effects between Achilles and control set will be compared in a mixed-effects (repeated-measures) linear model with *treatment* and *period* as fixed effects and *participant* as a random effect. Log-transformation will be applied if data distribution is found to be highly skewed.

The mean difference between treatments (or on the log-scale) will be compared with a two-sided test using significance level $\alpha=0.05$. Then mean ratio and its 95% confidence interval will be calculated

- Inverse-transforming will be done if the variable was log-transformed.

Secondary analyses will use the both ITT and PP populations for analysis. Multiple comparisons may raise these tests. We are not considering any correction in this SAP.

Population	ITT and PP (ITT is the primary , PP is the sensitivity)
------------	---

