Secondary Endpoints 1:	
Mean differences (within treatments over time and between treatments at specified time points) in:
 
 Time-to-Maximum Glucose Infusion Rate (GIR) ($t_{max(GIR)}$) Time to half-maximal GIR, both early and late ($t_{50(GIR),early}$ & $t_{50(GIR),late}$) Onset of action as measured by a drop of blood glucose (BG) by 5 mg/dL Duration of insulin action (calculated the same as MRT for PK) GIR_{max} Area under the GIR curve ($AUC_{0-t(GIR)}$), both absolute and as a percentage of total $AUC_{0-\infty}$ and Coefficient of Variation (CV) of $AUC_{0-t(GIR)}$, where $t = 5, 10, 15, 20, 30, 45, 60, 90, 120, 150, 180, 210, 240,$ and 300 min 
Other PD parameters may also be calculated.

Secondary Objective 2:	To assess pharmacokinetic (PK) parameters within and across treatments following subcutaneous delivery using Achilles vs Teflon control set on DOI and days 3, 5, and 7 post insertion.
Secondary Endpoints 2:	
Mean differences (within treatments over time and between treatments at specified time points) in:
 
 • Early exposure ($AUC_{0-60min}$) • Mean-residence time (MRT) of insulin • Maximum Insulin concentration (C_{max}) • Time-to-Maximum Insulin Concentration (t_{max}) • Time-to-50% Maximum Insulin Concentration [$t_{50,early}$ & $t_{50,late}$], both early (i.e. before C_{max}) and late (i.e. after C_{max}) • $AUC_{(0-t)}$ (both absolute and as a percentage of $AUC_{(0-300)}$) and Coefficient of Variability (CV) $AUC_{(0-t)}$ where $t = 3, 6, 9, 12, 15, 20, 25, 30, 35, 40, 45, 50, 60, 70, 80, 90, 105, 120, 150, 180, 210, 240$ and 300 min 
Other PK parameters may also be calculated.

Secondary Objective 3:	To assess continuous glucose monitoring (CGM) data, comparing data within and across treatments.
Secondary Endpoints 3:	
 • Mean daily time in range (70-180 mg/dL), DOI through Day 7 inclusive • Mean daily time in target (70-140 mg/dL), DOI through Day 7 inclusive • Mean and median daily glucose, DOI through Day 7 inclusive • Glucose variability (%CV), DOI through Day 7 inclusive • Mean daily time ≤ 70 mg/dL, < 54 mg/dL, DOI through Day 7 inclusive • Mean daily time > 140 mg/dL, > 180 mg/dL, > 240 mg/dL, DOI through Day 7 inclusive • Other CGM metrics may also be calculated
Secondary Objective 4:	To assess performance of investigational infusion set on DOI through 7 for each treatment

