The run-in period should last no longer than 3.5 hours, if BG is not stable after this time, the participant cannot continue in the study and is sent home. He/she may return another day. Once the BG level of approximately 95 ± 15 mg/dL has been maintained for at least 40 minutes (measured every 10 minutes), the IV insulin (dextrose) is discontinued, and the baseline will be recorded for 20 min (blood draw every 5 min). 20 minutes after discontinuation of IV insulin, a SC bolus of lispro insulin (0.15 U/kg) is administered via the pump (t0). Baseline plasma glucose level is defined as mean plasma glucose at time points t-20, t-15, t-10, t-5, and t0. After t0, blood samples for PK analysis are drawn every 3 minutes for 15 min (Clamp Part I), every 5 minutes for 40 minutes (Clamp Part II), every 10 min for 30 min (Clamp Part III), and every 15 minutes for 45 minutes. In the Final Phase, blood is drawn every half an hour until clamp termination at 300 minutes (see Table 6). Up to 15 blood samples will be obtained overnight prior to the day of the glucose clamp procedure, and 8 additional blood samples will be obtained during stabilization on the morning of the clamp procedure prior to administration of the insulin bolus. Blood samples for immediate glucose determination will be drawn every 5 minutes for 60 minutes following insulin bolus, and then every 10 minutes for the remainder of the clamping period at 300 minutes post-bolus. Blood samples will be acquired using aseptic technique and double stopcock technique to minimize blood loss. A maximum of 66 samples (24 x 1.5 mL [for BG and insulin] + 6 x 1.0 mL [for PK only] + 36 x 0.5 mL for BG only = 62.0 mL) will be drawn during the stabilization period and the clamp procedure, resulting in a total blood loss of 248 mL during 4 clamps over each week. Combining both

clamping weeks, this represents less than 1 unit of blood (=525 mL). Blood samples will be centrifuged to plasma, plasma glucose concentration measured, and plasma frozen in 2 aliquots for future measurement of insulin concentration. The detailed clamp sampling schedule is summarized in Table 6.

Table 6. Clamp visit sampling schedule

Phase	Approximate Clock Time (hh:mm)	Nominal Time (min)	No. of samples	Volume/Sample (mL)	Total Volume (mL)
Stabilization, over night			15	0.5	7.5
Baseline Part I	7:00	-60	5	0.5	2.5
	7:10	-50		0.5	
	7:20	-40		0.5	
	7:30	-30		0.5	
	7:40	-20		0.5	
Discontinue IV insulin & Dextrose					

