Baseline Part II	7:45	-15	3	1.5	4.5
	7:50	-10		1.5	
	7:55	-5		1.5	
Bolus	8:00	0	1	1.5	1.5
Clamp Part I	8:03	3	7	1	6.5
	8:05	5		0.5	
	8:06	6		1	
	8:09	9		1	
	8:10	10		0.5	
	8:12	12		1	
	8:15	15		1.5	
Clamp Part II	8:20	20	9	1.5	13.5
	8:25	25		1.5	
	8:30	30		1.5	
	8:35	35		1.5	
	8:40	40		1.5	
	8:45	45		1.5	
	8:50	50		1.5	
	8:55	55		1.5	
	9:00	60		1.5	
Clamp Part III	9:10	70	3	1.5	4.5
	9:20	80		1.5	
	9:30	90		1.5	
Clamp Part IV	9:40	100	10	0.5	8.0
	9:45	105		1	

Phase	Approximate Clock Time (hh:mm)	Nominal Time (min)	No. of samples	Volume/Sample (mL)	Total Volume (mL)
	9:50	110		0.5	
	10:00	120		1.5	
	10:10	130		0.5	
	10:15	135		1	
	10:20	140		0.5	
	10:30	150		1.5	
	10:40	160		0.5	
	10:50	170		0.5	
	11:00	180		1.5	
	11:10	190		0.5	
	11:20	200		0.5	
	11:30	210		1.5	
	11:40	220		0.5	
	11:50	230		0.5	
Final Phase	12:00	240	13	1.5	11.5
	12:10	250		0.5	
	12:20	260		0.5	
	12:30	270		1.5	
	12:40	280		0.5	
	12:50	290		0.5	
	13:00	300		1.5	
Observation at site			66 total samples		
				Total volume per clamp =	62.0 mL

During the 5-hour clamp plasma glucose concentration will be maintained at 95 ± 15 mg/dL with IV infusion of dextrose (0.1 to 4 mg/kg/min), titrated using a computerized dosing algorithm according to frequent BG measurements. The trigger plasma glucose concentration for onset of glucose infusion will be a value that is 5 mg/dL below the mean obtained during Baseline Part II (i.e. -15, -10 and -5 minutes before bolus delivery at T=0). The dosing calculator will be used to determine the optimal glucose infusion rate (GIR) for each subsequent time period between BG measurements. If insulin is infused, glucose infusion must be stopped and vice versa. The dextrose infusion rate will be increased to match insulin lispro's glucose lowering effect over time until the glucose lowering effect of the insulin lispro bolus reaches baseline (i.e. glucose infusion rate of 0) or 5 hours after bolus administration.

In the case of persistent hyperglycemia (BG > 250 mg/dL) over 30 minutes without dextrose infusion, the clamp will be terminated early. A correction bolus will be given via the pump and the BG measured to determine whether BG was lowered by 50 mg/dL within 1 hour. If this is not the case, the CSII catheter is

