9.4.3 ANALYSIS OF THE SECONDARY ENDPOINT(S)

Secondary analyses will use the both ITT and PP populations for analysis.

The survival of the Achilles and control infusion sets will be compared using a discrete lifetable analysis over study days 0, 3, 5, and 7 and the discrete form of the log-rank test.

All pharmacokinetic parameters (AUCs , t_{50} , C_{max} , t_{max} , MRT for the insulin concentration by time curve, etc.) will be estimated using non-compartmental models and log-transformed before analysis. Means for the two treatment groups will be compared in a mixed-effects (repeated-measures) linear model with treatment and period as fixed effects and participant as a random effect. The mean difference between treatments (on the log-scale) will be compared with a two-sided test using significance level $\alpha=0.05$. Then mean ratio and its 95% confidence interval will be calculated by inverse-transforming the mean difference and its 95% confidence interval.

All pharmacodynamic parameters (AUCs , onset time and time to return to baseline for the glucose concentration by time curve, etc.) will be estimated using non-compartmental models. Means for the two treatment groups will be compared in a mixed-effects (repeated-measures) linear model with treatment and period as fixed effects and participant as a random effect. The mean difference between treatments will be compared with a two-sided test using significance level $\alpha=0.05$. Wilcoxon signed rank tests will be used if the data is significantly skewed.

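### Early partial GIR AUCs are exactly zero until the clamp's dextrose trigger is reached, and the SAP's log-transform rule for skewed PD AUCs does not say what to do with zeros

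*SAP*

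**What the plan says.** **Endpoints.** The synopsis (Protocol 1.1, Secondary Endpoints 1) lists AUC0-t(GIR) "where $t = 5, 10, 15, 20, 30, 45, 60, 90, 120, 150, 180, 210, 240,$ and 300 min".

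**Clamp.** In Protocol 6.1.1.5, Table 6 has the step "Discontinue IV insulin & Dextrose" after the -20 min sample, so the infusion rate is zero at the bolus. The text after the table sets the restart: "The trigger plasma glucose concentration for onset of glucose infusion will be a value that is 5 mg/dL below the mean" of Baseline Part II. On sampling: "Blood samples for immediate glucose determination will be drawn every 5 minutes for 60 minutes following insulin bolus".

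**SAP analysis.** SAP 4.4.4.2.3 tests AUCs, t50, GIRmax, tmax(GIR) and duration of action in a mixed model with treatment and period. It adds "Log-transformation will be applied if data distribution is found to be highly skewed" and promises a mean ratio with a 95% interval. SAP 4.3.2.2 removes a profile whose infusion rates are all zero. SAP 4.2.1 makes no imputation the default.

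**Protocol analysis.** For PD parameters, Protocol 9.4.3 says: "Wilcoxon signed rank tests will be used if the data is significantly skewed". Protocol 9.4.1 allows PD data to be logged where appropriate and sends data that are still skewed after logging to a rank transformation. SAP 4.4.4.2.3 repeats neither rank provision, and SAP 2.5 (modifications from the protocol) does not mention the difference.

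**The concern.** A clamp that responds well at 25 min has AUC0-5, AUC0-10, AUC0-15 and AUC0-20 all equal to zero. The trigger rule produces these zeros; they are not recording errors. A cluster of zeros with a positive tail is strongly skewed, so these endpoints are the ones most likely to meet the SAP's condition for logging, on a scale where zero has no value. SAP 4.3.2.2 does not help, because the whole profile is not zero.

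The values lost would be those from slow-onset clamps. That loss depends on the outcome, so a missing-at-random argument cannot cover it. The comparison would become conditional on early response, and more clamps would go from whichever set is slower. Early partial AUCs are among the few tested PD measures of early action, beside t50 and tmax, because onset of insulin action is only described (SAP 4.4.4.2.4).

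**Working it through.** The documents give no figure for the partial GIR AUCs and no onset times, so there is nothing to reproduce. Onset values below are assumptions.

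**Check 1: arithmetic at t = 20 min.** Assume onset is normal with SD 7 min and mean 20 min (Achilles) or 25 min (control), and that the infusion rate then rises linearly, so AUC0-t is proportional to (t - onset)² when onset < t and is 0 otherwise. Let z = (t - mean)/7.

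- Share of zeros = 1 - Φ(z). Achilles: z = 0, 50%. Control: z = -0.714, 76%.
- All-clamp mean is proportional to 49 × [(z² + 1)Φ(z) + zφ(z)]. Achilles: 49 × 0.500 = 24.5. Control: 49 × 0.138 = 6.76. Ratio = 24.5/6.76 = 3.6.
- Ratio of non-zero shares = 0.500/0.238 = 2.1.
- Arithmetic ratio among non-zero clamps = 3.6/2.1 = 1.7.

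The all-clamp ratio is the product of the last two quantities, and dropping zeros discards the 2.1. Simulation with onset kept at or above 3 min and lognormal noise (0.3) gives 3.4 to 3.55 over all clamps, against 1.6 to 1.7 (arithmetic) or 2.0 (geometric) among non-zero clamps.

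Other times in the same scenario:

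- t = 10: zeros about 92% and 98%.
- t = 30: zeros 8% and 24%. The all-clamp ratio is about 2.2. Among non-zero clamps it is 1.8 (arithmetic) or 2.4 (geometric), so the direction depends on the scale.
- t = 45: zeros at most 0.2%.

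**Check 2: simulated crossover.** Assume lognormal onset with CV 40%, 60% of the log-variance between participants, medians 15 min (Achilles) and 20 min (control), the trigger detected at the 5-min samples, and four clamps per set. A participant-level paired t on logs with zeros missing is compared with the same test on ranks of all clamps, for n = 24:

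| t (min) | Zeros, Achilles / control | Pooled skewness | Participants positive with both sets | Power, log | Power, ranks |
|---|---|---|---|---|---|
| 10 | 100% / 100% | 12.9 | 0.0 | 0.00 | 0.00 |
| 15 | 85% / 96% | 4.1 | 2.1 | 0.01 | 0.78 |
| 20 | 50% / 78% | 2.9 | 10.5 | 0.45 | 1.00 |
| 30 | 9% / 28% | 1.5 | 22.0 | 0.99 | 1.00 |
| 45 | 1% / 4% | 1.0 | 23.9 | 1.00 | 1.00 |
| 60 | 0% / 0% | 0.9 | 24.0 | 1.00 | 1.00 |

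At n = 7, the number of completers when the study stopped (SAP 2.5), power is 0.06 (log) against 0.57 (ranks) at t = 20, and 0.56 against 0.85 at t = 30. With later medians of 20 and 30 min and n = 24, zeros are still 28% and 68% at t = 30, and power at t = 20 is 0.04 against 0.99.

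**Check 3: equal onsets.** With both medians at 15 min, the ratio with zeros dropped is 0.99 to 1.01 wherever it can be computed, and both methods reject in 0% to 6% of runs.

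**The case against.** **Dropout is inferred.** A reader might conclude that the SAP plans to discard slow-onset clamps. It does not say so. The log step is conditional, SAP 4.2.1 concerns blank values, and a computed zero is not blank. An offset or an untransformed model could still be chosen. This stands as a limit on the wording. Any such choice would be made after seeing the data, however, and the one rule that is written down fails on zeros.

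**Logging PD data is not new.** Protocol 9.4.1 allows it, and the silence of SAP 2.5 could mean the rank fallback still applies. That is fair. The documents leave it open, which is a reason to reconcile them.

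**Onset is measured elsewhere.** A reader might infer that the onset comparison itself is biased. SAP 4.3.2.4.3 defines onset as a separate time from glucose values; it is described and neither logged nor tested. Insulin AUC0-60 does not depend on the dextrose trigger.

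**Part of the apparent gap is a change of estimand.** Setting an all-clamp arithmetic ratio against a non-zero geometric ratio mixes two effects. The arithmetic comparison in Check 1 avoids this and still shows attenuation at 20 min.

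**The protocol's signed-rank test is not a full remedy.** The usual form discards zero differences and needs both periods. In the Check 1 scenario with four clamps averaged per set, about 70% of participants have zero with both sets at t = 10. With seven participants the chance of fewer than six non-zero differences is about 99% at t = 10 and 55% at t = 15. Five differences cannot give a two-sided p below 2/32 = 0.0625. This stands and shapes the fix.

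**The stakes are secondary.** These tests carry no multiplicity correction, the study stopped after seven completers, SAP 6 expects some outputs to be missing, and the descriptive summaries will still show the zeros. That limits the consequence but does not supply a rule.

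**Conclusion.** The concern holds for early partial AUC0-t(GIR), roughly t ≤ 30 min under the assumed onsets. The zeros are built into the clamp, the SAP's transformation rule cannot handle them, and no other SAP rule covers a zero partial AUC in a clamp that later responds. If the rule is followed, the main effect is to weaken a real early difference at about 15 to 20 min (a mean ratio of about 3.5 becoming about 1.7 at t = 20 for onsets of 20 and 25 min). At 5 and 10 min the log analysis is essentially inestimable. At 30 min the effect is smaller and its direction depends on the scale.

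The documents do not support a claim that Achilles would gain a false advantage, since equal onsets give a ratio of about 1. The primary AUC0-300, the later AUCs and the onset variable are untouched by these early zeros. The sizes rest on assumed onset times, spread and infusion ramp; the existence of the zeros and the missing rule do not.

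**What to change.** Amend SAP 4.4.4.2.3 as follows:

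- Do not log-transform any AUC0-t(GIR) endpoint that contains zeros.
- Analyse all clamps with the protocol's rank transformation inside the same mixed model, which keeps participants who have only one period. A permutation test on untransformed AUC0-t is an alternative, but swapping sets within participant uses only those with both periods.
- Report by set the proportion of clamps with AUC0-t above zero, with untransformed summaries.
- Present t = 5 and 10 min descriptively only.
- Keep ratios and their intervals for AUCs that are always positive.
- Record in SAP 2.5 how this relates to Protocol 9.4.1 and 9.4.3.

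The cost is SAP wording, with no new data. The price is that no ratio is reported for the earliest times and the rank result is not in units of glucose infused, which the proportion and the untransformed summaries partly make up for.
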